and increasing rates of breast conserving surgery (BCS) (68) Additionally, chemotherapy given prior to surgery allows for in vivo assessment of chemotherapy sensitivity. Patients who achieve a pathologic Complete Response (pCR), in which the tumor has been eradicated by chemotherapy prior to surgery such that there are no remaining viable invasive tumor cells at the primary tumor site and axillary lymph nodes in the surgical specimen, are known to have superior breast cancer-related and overall survival outcomes. (20) (21) Pathologic complete response rates have been used by the FDA to approve drugs; yet, there is a paucity of data regarding how lifestyle interventions affect this important outcome. Some studies have demonstrated that overweight/obese patients have a significantly lower pCR rate compared to patients who are normal/underweight (OR 0.67, 95% CI 0.45-0.99.), while other studies have found that overweight/obese women have lower pCR rates in ER+/HER2+ cancers but higher pCR rates in ER-/HER2+ cancers. (22) Our study will allow us to investigate pCR rates in those who receive a healthy diet and physical activity intervention compared to those who do not. Further, we will control for meaningful covariates including initial BMI, chemotherapy regimen and completion rates, and tumor receptor status. There is a recognized need to evaluate the functional, endocrinologic, and immunologic end points associated with lifestyle modifications and the effects of these on response to therapy. (23)

Lifestyle Interventions and Cancer Biomarkers in Breast Cancer Survivors: We recently completed the Lifestyle, Exercise and Nutrition (LEAN) 6-month randomized trial of healthy eating and exercise in 100 women (of 825 screened, 12%) who had completed treatment for breast cancer. (24) The 11-session intervention (conducted in person or via telephone) was adapted from the 2010 U.S. Dietary Guidelines, ACS and AICR guidelines 1-3 and modeled on the diabetes prevention program. We found statistically significant decreases in body weight among women randomized to intervention (-6% mean weight loss) compared to usual care (-2.0% mean weight loss) ($p = .0024$), and a 30% decrease in CRP ($p = .05$) and 10% decrease in insulin ($p = 0.08$) compared with no changes in usual care. Favorable dietary changes were observed as well (see Goals of Intervention section for results on page 10).

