Women will be asked to complete the self-administered study questionnaires prior to the in-person baseline visit. They will be provided a link via email to the online questionnaires or given a hard copy version if preferred.

Assessments	Screening	Baseline	Post-chemo	1-year	2-year	5-year
Screening Questionnaire	X					
Demographic Questionnaire*		X				
Medical History Questionnaire*		X				
Food Frequency Questionnaire		X	X	X	X	X

Phone assessment 24-hour dietary recall – 1-day ^{&1}		X	X	X	X	
Physical Activity Questionnaire		X	X	X	X	X
Patient Global Assessment (SGPGA)	X					
PROMIS quality of life questionnaires(74)		X	X	X	X	X
Prescription Medication		X	X	X	X	X
Adherence to medication questionnaire(75, 76)				X	X	X
Neuropathy – EORTLC QLQ-CIPN20(77)		X	X	X	X	X
Work history			X	X	X	X
Beliefs about Medication Questionnaire(78)				X	X	X
Treatment Satisfaction Questionnaire for Medication(79)				X	X	X
Health Insurance, prescription coverage and prescription refill habits				X	X	X
Medication usage questionnaire				X	X	X
Aromatase Inhibitor/Tamoxifen usage form				X	X	X
Breast Cancer Prevention Trial (BCPT) Symptom Scales (80)		X	X	X	X	X
Brief Pain Index		X	X	X	X	X
Homunculus		X	X	X	X	X
Y5-Lymphedema Questionnaire						X
Supplement intake/over the counter medication *		X	X	X	X	X
Y1 -Lymphedema Questionnaire				X		
Y2- Lymphedema Questionnaire					X	
Satisfaction Questionnaire (Intervention group)				X		
Side-effects and toxicity assessment (PRO-CTCAE™)		X	X			
Chemotherapy delay/dose reduction/reasons (extracted from EPIC EMR)			X			
Grip Strength [%]		X	X	X	X	
EPIC 2YR follow up treatment form					X	

EPIC 5 Year medical usage and breast cancer status abstraction						X
Two Year Follow up Treatment form'					X	
Height and weight measured [%]		X	X	X	X	
Waist and hip circumference measured [%]		X	X	X	X	
Blood collection [%]		X	X	X	X	
DXA scan [%]		X	X	X	X	
Urine collection ^{%@}				X	X	
Urine collection for pregnancy test if applicable prior to DEXA [%]		X	X	X	X	
Stool collection [%]		X	X	X		
Skin carotenoids [%]		X	X	X	X	

*: Part of the Baseline Questionnaire

%: Applicable only to the Yale site when in-person visits are completed. Assessments are optional.

@ Applicable to women who are prescribed an aromatase inhibitor

&: Assessment is optional.

1: Discontinued in August 2020.

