Participants who report that they have discontinued taking tamoxifen or AI will also be classified as nonadherent to endocrine therapy. For patients who may be lost to follow-up, we will obtain prescription refill data as an endpoint of adherence to endocrine therapy. For the endocrine

therapy aim, we will compare the crude adherence rates using simple logistic regression. Multivariate logistic regression will serve as supportive analyses including covariate adjustments – which are similar to the primary analysis above.

The secondary aims will be performed using Mixed Model Repeated Measures analysis incorporating Analysis of Covariance, where each woman's changes in outcome (follow-up measure – baseline) will be modeled as a function of treatment and time with a covariate included for the baseline value. Prior to fitting models, we will perform exploratory data analyses focusing on the distributions of biological markers by time and intervention group, assessing the appropriateness of log-transformation.

All hypotheses will be tested according to the intention-to-treat philosophy in which all randomized participants will be grouped according to their intervention assignment at randomization, regardless of compliance or adherence to the study. Statistical significance will be defined as $p < 0.05$, 2-sided. Since we have multiple outcomes, we will consider using a Bonferroni correction.

Age, menopausal status, race/ethnicity, BMI at diagnosis, disease stage, type of surgery, type of chemotherapy, radiation therapy, hormone receptor status, endocrine therapy, reconstructive surgery, type 2 diabetes, and smoking status will be examined as covariates. We will explore effect modification by menopausal status at diagnosis, hormone receptor status, and endocrine therapy.

We will further explore intervention effects on study endpoints by stratifying by adherence to diet and physical activity guidelines with a four-level category (e.g., met diet recommendations, met physical activity, met both diet and physical activity recommendations, or met neither recommendation). This analysis will allow us to better understand the role of diet vs. exercise on study endpoints.

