Although we do not anticipate an appreciable number of subjects lost-to-follow-up because of our plan of following patients during their medical oncology visits, the impact of missing data will be evaluated in the analysis. Bivariate logistic regression will be used to identify baseline variables associated with missingness. The primary analysis assumes missing data are missing at random (MAR). Under the MAR missing data mechanism, the probability of loss-to-follow-up depends only on the observed data. Non-random or informative loss-to-follow-up occurs when the missing data are dependent on the unobserved missing outcome values, latent and/or instrumental variables. Sensitivity analyses using methods for NMAR data will be considered.

Power and Sample Size Considerations: The sample size estimate was performed using PASS 12 (©2013 NCSS, LLC, Kayesville, UT). The original calculation was based on chemotherapy completion rates reported in the COMPAS study (Ziller etc, BMC Cancer, 2013). By assuming similar completion rate in our control arm, we estimated a sample size of 250 subjects would be needed. Sample size reevaluation was conducted using the aggregated data of first 51 LEANer participants who completed chemotherapy. The pooled standard deviation of RDI is 0.10. We re-estimated that a sample size of 86 subjects per arm (172 total) will achieve 90% power to detect a 0.05 (or 5%) difference in RDI between two arms at significance level of 0.05. For endocrine therapy adherence, the COMPAS study reported 48% of patients in the control group were adhering to AI therapy at 12 months.¹⁸ We assume approximately 50% of patients randomized to usual care in our study will be adhering to endocrine therapy at one-year post-initiation of use. Group sample sizes of 76 patients per group (or $N = 152$) provides 90% power to detect an absolute difference of 25% in the intervention group (50% vs. 75%, adherence in control and intervention groups, respectively) at a two-sided 0.05 significance level. We anticipate ~70% of participants (i.e., 70% of 172 = 120) will be prescribed endocrine therapy; thus an $N = 120$ will also allow for sufficient statistical power.

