For insulin, our previous studies showed a 25-30% effect size (3.0 μ U/mL) and standard deviation of 8.0 μ U/mL, which yields a per group sample size of 112 or total N = 224.24 For weight changes, our LEAN study showed a 7% effect size (5.6 kg) and a SD of 4.2 kg in the intervention group compared to 2% (1.7 kg) and SD of 3.7 kg in usual care (P=0.0004). (24) We will have sufficient statistical power to detect smaller effect size since we will have a larger sample size in the current application.

We will not allow participants who are assigned into usual care cross over to intervention group. However, if 10% of 86 participants who are randomized into intervention arm drop out to usual care, we will have 81% power to detect difference of 18% chemotherapy dose adjustment in intervention vs 34% in controls.

SECTION II: RESEARCH INVOLVING DRUGS, BIOLOGICS, RADIOTRACERS, PLACEBOS AND DEVICES

If this section (or one of its parts, A or B) is not applicable, state N/A and delete the rest of the section.

A. RADIOTRACERS – N/A

B. DRUGS/BIOLOGICS – N/A

B. DEVICES – N/A

SECTION III: RECRUITMENT/CONSENT AND ASSENT PROCEDURES

1. Targeted Enrollment: Give the number of subjects:

- a. Targeted for enrollment at Yale for this protocol: 133
- b. If this is a multi-site study, give the total number of subjects targeted across all sites: 172

2. Indicate recruitment methods below. Attach copies of any recruitment materials that will be used.

- | | | |
|--|--|-------------------------------------|
|  Flyers |  Internet/Web Postings |  Radio |
|  Posters |  Mass E-mail Solicitation |  Telephone |
|  Letter |  Departmental/Center Website |  Television |
|  Medical Record Review* |  Departmental/Center Research Boards |  Newspaper |
|  Departmental/Center Newsletters |  Web-Based Clinical Trial Registries | |
|  YCCI Recruitment database |  Clinicaltrials.gov Registry (do not send materials to HIC) | |

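### The stated insulin requirement of 224 women exceeds the 172 enrolled and the roughly 133 at most who can give blood; on the plan's own unadjusted inputs, power is about 69% and 57% respectively

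*Combined protocol and SAP*

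**What the plan says.** Insulin is one of three biomarkers in secondary Aim 2a. In Section I, item 12 (Power and Sample Size Considerations), the plan assumes a difference of 3.0 µU/mL and a "standard deviation of 8.0" µU/mL, "which yields a per group sample size of 112", 224 in total. No power is attached to that number. The significance rule in the same item reads "Statistical significance will be defined as $p < 0.05$, 2-sided".

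The same section explains that the trial was first sized at 250. It was re-sized at 86 per arm, 172 in all, from the pooled SD of RDI in the first 51 women to complete chemotherapy. Insulin played no part in that re-evaluation.

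On who gives blood:
- The footnote to the assessment table (Section I, item 3(c)) marks blood collection as "Applicable only to the Yale site when in-person visits are completed. Assessments are optional".
- The Biomarkers paragraph restricts blood to Yale in-person visits, and Experimental Design makes those assessments optional at every time point.
- The second recruiting site, Dana Farber, does no in-person assessments.
- A note under the table says in-person assessments stopped in mid-March 2020, to resume when the institution allows.
- Section III, item 1 gives "Targeted for enrollment at Yale for this protocol: 133", out of 172 across all sites.

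**The concern.** A sample size of 224 cannot be met by a trial of 172, and no section acknowledges the gap. The insulin sentence appears to have been left behind when the trial was reduced. The Randomization paragraph likewise still allocates 125 women to each arm.

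The number who can supply insulin data is smaller again, because blood depends on site, on an optional visit and on the pandemic pause. A reader who takes 224 at face value could treat a null insulin result as more informative than the data allow.

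**Working it through.** **Inputs.** Difference Δ = 3.0 µU/mL, SD σ = 8.0 µU/mL and two-sided α = 0.05 (Section I, item 12); 1:1 allocation (Randomization); 172 women overall and 133 at Yale (Section III, item 1).

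**Step 1: reproduce the plan's figure.** n per group = 2(z₀.₉₇₅ + z_power)² σ²/Δ². At 80% power this is 2 × (1.960 + 0.842)² × (8/3)² = 2 × 7.849 × 7.111 = 111.6, so 112. The exact t-test version gives 112.6. Other conventions do not give 112: 85% power needs 128, 90% needs 150, one-sided 80% needs 88 and one-sided 90% needs 122. The stated size therefore implies 80% power, two-sided.

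**Step 2: power at the numbers now available.** Power ≈ Φ(Δ/(σ√(2/n)) − 1.960), checked against the noncentral t.

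| Women with usable insulin data | n per arm | Normal | t-test |
|---|---|---|---|
| 224 (stated) | 112 | 80.1% | 79.8% |
| 172 (everyone enrolled) | 86 | 69.1% | 68.6% |
| 133 (all of Yale's target) | 66.5 | 58.0% | 57.4% |

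For example, at 86 per arm: 3/(8 × √(2/86)) = 2.459; 2.459 − 1.960 = 0.499; Φ(0.499) = 0.691.

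**Step 3: difference detectable with 80% power.** σ√(2/n) × 2.802 gives 8 × 0.1525 × 2.802 = 3.42 µU/mL at 86 per arm and 8 × 0.1734 × 2.802 = 3.89 µU/mL at 66.5 per arm.

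**Step 4: losses among the 133.** The documents give no rate for missed blood draws. With assumed losses of 10%, 20% and 30%, t-test power is about 53%, 48% and 43%.

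**Step 5: baseline adjustment.** The planned analysis is a mixed model on change with the baseline value as covariate. If 8.0 is the SD of raw values, the residual SD is 8.0√(1 − ρ²), where ρ is the correlation between baseline and follow-up. The documents give no ρ. At an assumed 0.5, the residual SD is 8.0 × √0.75 = 6.93, and normal-approximation power is about 81% with 172 women and 70% with 133. Reaching 80% needs ρ of about 0.48 with 172 women (residual SD 7.02) or 0.64 with 133 (residual SD 6.17).

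If 8.0 is instead the SD of change, and the variance is equal at both times, the residual SD is 8.0√((1 + ρ)/2). The two readings agree at ρ = 0.5 but separate above it. At ρ = 0.64 the change reading gives 8.0 × √0.82 = 7.24. With 133 women that is 3/(7.24 × √(2/66.5)) = 2.389, and Φ(2.389 − 1.960) is about 67%, not 80%. What the SD refers to therefore matters.

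**The case against.** The strongest reply is that the unadjusted comparison is not the planned analysis. Baseline adjustment could recover much of the loss, and with all 172 women a moderate correlation would restore 80%. This stands as a reason not to quote 57% to 69% as the trial's actual power. It does not rescue the sentence, because the plan's own calculation uses no adjustment and gives no correlation.

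Second, insulin is secondary, and the trial is sized on RDI. A reader might infer that the trial is presented as powered for insulin. The documents do not support that: no insulin power is stated, and the later remark about sufficient power follows the weight example.

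Third, a reader might infer that the assumed effect of 25% to 30% contradicts the Background, which reports a "10% decrease in insulin" in the LEAN trial, the programme this intervention adapts. That reading is selective. The plan attributes its assumption to previous studies in the plural. The Background section on exercise trials reports a 28% reduction in one of the group's trials, 20% relative to controls in another, and −14.5% against +20.7% in newly diagnosed women. The present intervention also runs 12 months rather than 6 and adds strength training. The assumption may prove optimistic, but it is not inconsistent with the Background.

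Fourth, 133 is approximate. The documents do not say whether women who self-refer from Columbia count within it. Women enrolled remotely may choose later in-person visits, but without a baseline sample they add little to an analysis of change from baseline. The pandemic stoppage was a pause, not an end.

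Fifth, the consent-waiver text in Section III says the genetic analysis was added after all relevant women were off study. Blood collection for those women was presumably over, so prospective power now matters less than how the result is reported.

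**Conclusion.** The point holds as an error in a stated figure. The 224 reproduces, but it exceeds total enrolment by 52 women (224 − 172) and Yale's whole target by 91 (224 − 133). On the plan's own unadjusted inputs, about 69% power is the most that 172 women could give, and about 57% corresponds to blood from every woman in Yale's target; optional or missed draws would lower the latter. Baseline adjustment could raise both by an amount the documents do not allow one to fix. The mismatch between 224 and 172 is certain; any single power value is conditional on the SD, the correlation and the number of women with paired samples. The primary sizing is not touched: 86 per arm does give 90% power for a 0.05 difference in RDI with SD 0.10. This is a correction that should be made, not a flaw in the design.

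**What to change.** Replace the 112/224 sentence with the power, or the detectable difference, for the number of women expected to have both baseline and follow-up blood. If sampling is complete, use the number who do. On the present inputs that means about 57% power, or a detectable difference of about 3.9 µU/mL, with 133 women; the 172-woman figures (69%, 3.4 µU/mL) apply only if everyone gave blood. State whether the SD of 8.0 is for raw values or for change, and give the source of any baseline correlation used to claim more. Report insulin as an estimated difference with a confidence interval, not as a comparison with 224 women behind it.

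The cost is the rewording of one paragraph and a less favourable figure in print. Enrolment, procedures and the primary analysis do not change.

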Lifestyle Interventions and Chemotherapy Completion Rate: Few studies have examined how lifestyle behaviors may impact chemotherapy completion rates. A recent publication by van Waart et al evaluated the effect of a home-based, low-intensity physical activity program (Onco-Move) and a supervised, moderate- to high-intensity, combined resistance and aerobic exercise program (OnTrack) compared to usual care on chemotherapy completion rates (i.e., the percentage of patients who would complete chemotherapy without dose adjustments assessed via medical records)(8) The planned chemotherapy regimens and schedules of the three groups were similar and included combinations of anthracyclines, taxanes, alkylating agents, and antimetabolites. In total, 61 of 230 patients (27%) required chemotherapy dose adjustments, with a smaller percentage of OnTrack participants requiring chemotherapy dose adjustments (12%) than those in the Onco-Move (34%) or usual care group (34%), $p = .002$. The average dose reduction among those who required chemotherapy adjustment in OnTrack and Onco-Move was 10%, compared with 25% in usual care; $P=.014$, with neuropathy being the main reason for dose adjustments.

This study was the first to replicate the previously observed positive effect of exercise on chemotherapy completion rates in Courneya and colleagues' exercise intervention trial in 242 breast cancer survivors initiating adjuvant chemotherapy.(9) Women were randomly assigned to usual care ($n = 82$), supervised resistance exercise ($n = 82$), or supervised aerobic exercise ($n = 78$) for the duration of their chemotherapy (median, 17 weeks; 95% CI, 9 to 24 weeks). While the primary endpoint was quality of life, a secondary endpoint was chemotherapy completion rate. Adjusted mixed-models analyses indicated that resistance exercise was superior to usual care for improving chemotherapy completion rate ($p=.033$). Relative dose-intensity was 84% in the usual care group compared with 90% in the resistance-training group ($P=.033$) and 87% in the aerobic exercise group ($P = .266$). The percentage of

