The MethylationEPIC BeadChip (Illumina; San Diego, CA) will allow us to interrogate >800,000, methylation sites quantitatively across the genome at the Yale Center for Genome Analysis. A sample of pooled female DNA is routinely included on each BeadChip as a control throughout the experiment and assessed for reproducibility using a Pearson R² coefficient. We will set to missing data points with detection p-values >.001 and will exclude any samples with probe detection call rates < 95% as well as those with an average intensity value of either <50% of the experiment-wide sample mean or < 2000 arbitrary units (AU). To limit confounding due to positional effects, samples for each person will be run in the same row.

P16 Human p16 ELISA Kit (LSBio) will be used according to manufacturer's instructions.

***Stool collection:** A stool collection kit, collection and mailing instructions will be provided to each participant to collect a stool sample in their home as baseline, post chemo and 1-year. Stool will be returned by pre-paid Fed Ex delivery to the Yale School of Public Health. Samples will be frozen and then sent for analysis to outside laboratories (Metabolon and [name] at UCSD). Women who are randomized after their first chemotherapy session (but prior to their second session) will not be asked to complete the stool collection at baseline or thereafter as their stool microbiota may have been affected by the chemotherapy so change in microbiota would be uninterpretable.

Analysis of Chemotherapy Completion Rate: Chemotherapy completion rate will be assessed (via medical records in EPIC) as the average relative dose-intensity (RDI) for the originally planned regimen

based on standard formulas. We will measure the number and percent of patients requiring dose-adjustments, who have dose-delays, the reason for the dose-adjustment/dose delays (e.g. neuropathy or vacation) and the percent dose reduction for each participant and by group, similar to Courneya and van Waart's papers.(8, 9) All relevant data will be extracted from EPIC (electronic medical records).

Analysis of Pathologic Complete Response: Pathology reports will be used to evaluate residual tumor after neoadjuvant chemotherapy. Pathologic complete response will be defined as no evidence of viable invasive tumor cells at the primary tumor site and axillary lymph nodes in the surgical specimen, regardless of the presence of non-invasive breast cancer or DCIS (Tis); i.e., yT0/TisN0.

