Relative dose intensity will be calculated using the methods described by Longo et al [24]. The primary endpoint, RDI will be analyzed both as a continuous scale using the t test, and as a dichotomized outcome using 85% or 95% cut-off for Mantel-Haensel chi-square test controlling for stratification factors. In addition, group differences in chemotherapy completion rates will be analyzed with binary logistic regression analysis; whether or not having dose reduction during the period of chemotherapy treatment (the period between T0 and T1) will be the dichotomized dependent variable. The outcome of endocrine therapy adherence will be assessed at the 2 and 5-year follow ups (as most, if not all, participants prescribed endocrine therapy will have been taking it for at least 1 year at the 2-year visit, allowing us to assess adherence to endocrine therapy). The primary endocrine therapy outcome will be adherence to endocrine therapy assessed via the electronic medical records. Note: the assessment for the primary outcome of endocrine therapy adherence was changed from the initial assessment (urinary metabolites) as the COVID pandemic limited our ability to collect urine samples.

Secondary assessments of endocrine therapy will be:

a) Urinary AI level. An undetectable level will classify the participant as nonadherent to AIs.

b) Responses to the following questions:

(1) “In the past month, how often did you take your medications as the doctor prescribed?” Possible responses are all of the time (100%), nearly all of the time (90%), most of the time (75%), about half the time (50%), or less than half the time (<50%). Nonadherence is defined as 75% of the time or less.

(2) “In the past month, how often did you forget to take 1 or more of your prescribed medications?”

Possible responses were never, once in the past month, 2 to 3 times in the past month, once per week, several times per week, and nearly every day. Nonadherence is defined as forgetting to take prescribed medications once per week or more.

(3) “In the past month, how often did you decide to skip 1 or more of your prescribed medications?”

Possible responses were the same as for question 2. Nonadherence is defined as deciding to skip medications once per week or more. The first will be the primary measure of non-adherence. (73,74).

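### The 81% power stated for dose adjustment (18% vs 34%) does not hold at 86 per arm: it is about 67%, or about 57% if 18% is the rate before drop-out

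*Combined protocol and SAP*

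**What the plan says.** All of this is in Section I of the combined protocol and SAP unless noted.

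- **Power claim** (item 12, Power and Sample Size Considerations). The premise is "if 10% of 86 participants who are randomized into intervention arm drop out to usual care", and the claim is that "we will have 81% power to detect difference of 18% chemotherapy dose adjustment in intervention vs 34% in controls". Cross-over from usual care to the intervention is not allowed.
- **Trial size** (same subsection). The first calculation is reported as "we estimated a sample size of 250 subjects would be needed". After a re-estimate from the pooled RDI standard deviation of 0.10, "a sample size of 86 subjects per arm (172 total) will achieve 90% power" for a difference of 0.05.
- **Analysis** (item 12, Statistical Analyses). "The primary endpoint, RDI will be analyzed both as a continuous scale using the t test", and also dichotomised. Dose reduction during chemotherapy has its own logistic regression. Significance is two-sided 0.05, and "all randomized participants will be grouped according to their intervention assignment at randomization, regardless of compliance or adherence to the study".
- **Data source** (item 3 c, Analysis of Chemotherapy Completion Rate). "All relevant data will be extracted from EPIC (electronic medical records").
- **Origin of the rates** (item 2, Background). One exercise trial is reported with a smaller share of its supervised arm "requiring chemotherapy dose adjustments (12%) than those in the Onco-Move (34%) or usual care group (34"%). The 34% matches this trial's usual care arm. No source is given for 18%.
- **Aim** (item 1). The number of dose reductions is listed within primary Aim 1a.

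**The concern.** The sentence cites 86 per arm, but 81% looks too high for a 16-point difference at that size. Item 3 d (Randomization) still allocates 125 women to each arm, which suggests that the power text may not have been fully updated when the total fell from 250 to 172.

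The sentence also leaves open whether 18% is the rate among women who stay on the intervention or the rate in the whole arm once drop-outs are included. Under intention to treat the two give different power.

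What is at stake is interpretation. Dose reductions belong to a primary aim. A non-significant comparison read against 81% power would count as fairly strong evidence against a 16-point effect. With true power of 67% or 57%, the trial would miss that effect about one time in three, or more than two times in five, instead of about one time in five.

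**Working it through.** **Inputs.** 86 per arm, 18% vs 34%, 10% drop-out to usual care (item 12, power subsection); two-sided 0.05 and intention to treat (item 12, analyses). Outcomes come from medical records and women are analysed as randomized, so drop-outs stay in the intervention arm and both arms stay at 86.

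**Formula.** Two-proportion z test without continuity correction, D = p2 − p1:

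- pooled: power = Φ[(D − 1.96·s0)/s1]
- unpooled: power = Φ[D/s1 − 1.96]
- s0 = √[p̄(1 − p̄)(1/n1 + 1/n2)]; s1 = √[p1(1 − p1)/n1 + p2(1 − p2)/n2]

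**Check on the figure that sizes the trial.** RDI: d = 0.05/0.10 = 0.50, 86 per arm, noncentral t, power 90.3%. The stated 90% reproduces.

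**Reading A: 18% is the rate after drop-out.** The rate before drop-out would then be (0.18 − 0.1 × 0.34)/0.9 = 0.162.

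- p̄ = 0.26; s0 = 0.0669; s1 = 0.0658; D = 0.16
- pooled: (0.16 − 1.96 × 0.0669)/0.0658 ≈ 0.44, power 67.0%
- unpooled: 0.16/0.0658 − 1.96 ≈ 0.47, power 68.2%
- exact enumeration of the chi-square test: 67.8%

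**Reading B: 18% is the rate before drop-out.** Under intention to treat the arm's rate becomes 0.9 × 0.18 + 0.1 × 0.34 = 0.196.

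- s0 = 0.0675; s1 = 0.0666; D = 0.144
- pooled: about 0.17, power 56.9%
- unpooled: about 0.20, power 58.0%
- exact: 57.6%

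**Can another method rescue 81% at this size?** With 18% vs 34%:

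| Variant | Power |
|---|---|
| Drop-outs removed, 77 vs 86 | 64.1% pooled, 66.2% unpooled |
| Drop-outs regrouped with usual care, 77 vs 95 (contrary to intention to treat) | 65.9% pooled, 68.7% unpooled |
| Continuity-corrected, 86 vs 86 | 60.4% |
| Fisher exact, 86 vs 86 | 60.8% |
| One-sided 0.05, 86 vs 86 (contrary to the plan) | 77.6% pooled, 78.5% unpooled |
| Superseded size less 10%, 112 vs 125 | 80.3% pooled, 80.5% exact, 81.8% unpooled |
| Superseded size less 10%, 113 vs 125 | 80.5% pooled, 81.1% exact, 81.9% unpooled |

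Only the old arm size reproduces the stated figure.

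**Size needed for 81%.** Reading A needs about 117 (unpooled) to 120 (pooled) per arm. Reading B needs about 148 to 151.

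**RDI under the same dilution.** d = 0.9 × 0.50 = 0.45 at 86 per arm gives 83.5%.

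**Minor item, insulin.** The plan gives a difference of 3.0 µU/mL, an SD of 8.0 and a total of 224. With d = 3.0/8.0 = 0.375 and 112 per group, unadjusted power is 79.8%, so 224 corresponds to 80%. The trial enrols 172. Blood is optional and taken only at Yale in-person visits, and Section III, item 1 targets 133 women at Yale. At 67 vs 66, unadjusted power is 57.4%, and the difference detectable at 80% power is 3.92 µU/mL. Some Yale women may enrol without in-person visits (Section III, item 6), so 133 is a ceiling.

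**The case against.** The strongest counter-argument is about wording: 18% could be read as a difference, that is 16% vs 34%. At 86 per arm that gives 78.3% pooled and 79.6% unpooled, only 1 to 3 points short. But the sentence sets a figure for the intervention arm beside a figure for controls, so reading 18% as a rate is much more natural. The difference reading still does not reach 81%. If 16% were the rate before drop-out, dilution to 0.9 × 16% + 0.1 × 34% = 17.8% brings power back to 68-69%. What stands is that the range of 57% to 68% depends on 18% being the intervention-arm rate, and the corrected sentence should say so.

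Second, RDI is named as the primary endpoint and sizes the trial; the dose-reduction regression is additional. That is true and limits the consequence to how one comparison is interpreted. Enrolment would not change.

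Third, the power sentence speaks of dose adjustment while the regression models dose reduction, and the assessment section lists adjustments, delays and percent reduction separately. They may not be the same events. The arithmetic does not depend on this, but the power statement should name the outcome it refers to.

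Fourth, carry-over from 250 is an inference. It is offered only as a likely explanation, and the error does not rest on it.

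Fifth, the 57% for insulin is unadjusted, whereas the planned model adjusts for baseline and could do better. That is correct; the plan states no correlation from which to judge by how much.

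**Conclusion.** The stated 81% is wrong for the 86 per arm that the sentence itself cites. Taking 18% as the intervention-arm rate, with two-sided 0.05, women analysed as randomized and outcomes available on all 172, power is about 67-68% if that rate already includes drop-out and about 57-58% if it does not. The shortfall is about 13 to 24 points, more than the choice of two-sided test or rounding can explain. It concerns a component of primary Aim 1a. It does not touch the RDI calculation, the sample size, the analysis or alpha, so it should be fixed but does not threaten the design. The insulin total and the outdated allocation count are minor and do not bear on this conclusion.

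**What to change.** In item 12, replace 81% with about 67%, or with about 57% if 18% is the rate before drop-out. State that 18% is the intervention-arm rate, whether it is before or after drop-out, and which outcome it describes (dose adjustment or dose reduction). Optionally add that RDI power under the same 10% dilution is about 84%, which shows that the endpoint sizing the trial tolerates the drop-out.

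Minor, at the same time:

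- Beside the insulin total of 224, say that it is not met, and give the unadjusted power or detectable difference at the number of women expected to give blood (at the ceiling of 133: about 57%, or 3.9 µU/mL at 80% power). If the baseline-adjusted model is relied on to improve this, state the assumed correlation.
- In item 3 d, change 125 + 125 to 86 + 86.

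The cost is a few words. No patients are added, and neither the analysis nor alpha changes. The only drawback is a less favourable power figure.
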